1.1 Background

Malignant melanoma is a virulent disease claiming almost 8600 patients annually in the United States.(1) the median survival with metastatic disease is usually less than one year. Systemic therapies are largely ineffective in this disease and there are no approved therapies beyond first line treatment.(2) In 2010 Hodi, et al, published the first phase III randomized trial demonstrating a survival benefit in metastatic melanoma using the immunotherapeutic agent ipilimumab, an anti-CTLA-4 antibody.(3) This was a multi-institutional randomized, double-blind phase III trial in previously treated patients with a diagnosis of unresectable stage III or IV melanoma. Patients were randomized in a 3:1:1 ratio, to treatment with an induction course of ipilimumab, at a dose of 3 mg per kilogram of body weight, plus a gp100 peptide vaccine; ipilimumab plus gp100 placebo; or gp100 plus ipilimumab placebo — all administered once every 3 weeks for four treatments. The median overall survival was 10.0 months among patients receiving ipilimumab plus gp100, as compared with 6.4 months among patients receiving gp100 alone (hazard ratio for death, 0.68; P<0.001). The median overall survival with ipilimumab alone was 10.1 months (hazard ratio for death in the comparison with gp100 alone, 0.66; P = 0.003). No difference in overall survival was detected between the ipilimumab groups (hazard ratio with ipilimumab plus gp100, 1.04; P = 0.76). Grade 3 or 4 immune-related adverse events occurred in 10 to 15% of patients treated with ipilimumab and in 3% treated with gp100 alone. The best overall response rate was 5.7% and 10.9% in the two ipilimumab arms. Although these results are promising, the fact that only approximately 10% of patients responded to ipilimumab suggests that this strategy is not effective for all patients with metastatic disease.

Mechanism of action of ipilimumab and relevance for melanoma

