
SBRT in the setting of metastatic disease

SBRT is being used increasingly in the setting of metastatic disease. Initially, it was integrated as an ablative approach with a goal of tumor sterilization in oligometastatic disease with minimal morbidity and good long-term clinical outcome in these highly selected patients.(15-17) Subsequently, data have emerged that SBRT provides effective palliation in the metastatic setting for palliation of bone, lung, liver, and subcutaneous/nodal metastases with minimal morbidity.(15, 16, 18-20) As such, SBRT is being increasingly utilized in the metastatic setting for palliative intent.

SBRT and Immune Activation

There is emerging evidence that hypofractionated radiotherapy is immunostimulatory. In a recently published study in *Blood*, Lee et al demonstrated that the therapeutic effect with ablative hypofractionated radiotherapy was dependent upon activation of CD8+ T-lymphocytes.(21) Additionally, there are pre-clinical data to suggest that CTLA-4 blockade along with ablative radiotherapy to an index lesion can prevent metastatic dissemination of disease.(22, 23) Finally, there are clinical data to suggest that SBRT provides greater local control and a reduction in regional and distant dissemination of disease when compared with surgery alone in NSCLC. One hypothesis to explain these surprising data is that the

CONFIDENTIAL

This material is the property of the study sponsor. Do not disclose or use except as authorized in writing by the study sponsor

Printed on 1/31/2017

immunostimulatory effect of SBRT results in improved control of disease and prevention of spread.(24)

Summary

We propose a stratified phase I/II clinical trial of SBRT to an isolated index lesion followed by ipilimumab in patients with previously untreated or previously treated metastatic melanoma in patients eligible for CTLA-4 blockade. In our protocol, the goal is to “vaccinate” patients against their melanoma via SBRT and then to elaborate the induced immune response with the FDA-approved CTLA-4 blocking antibody ipilimumab.

2 Study Objectives

The overall objective of the study is to determine the feasibility of delivery of SBRT to an index lesion in patients with metastatic melanoma prior to standard of care immunotherapy with ipilimumab.

Primary Objective

The primary objectives are to determine feasibility and immune-related clinical responses associated with SBRT when given in conjunction with ipilimumab.

Secondary Objective

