5.2 Dose Limiting Toxicities Definitions

Dose-limiting (Acute) Toxicity is defined as any treatment related Grade 4 or higher immune-related toxicity or Grade 3 or higher non-immune related toxicity which is observed during treatment or within 30 days of the final ipilimumab injection **and** which is probably or definitely related to radiation treatment. This definition will be used for de-escalation to the -1 dose level. All toxicities will be graded by NCI CTC Version 4.0.

Late toxicity Late toxicities will be graded according to the RTOG/EORTC late morbidity scoring system. The time frame for late toxicity is open-ended and late toxicities have been known to occur a year or more after therapy. Follow-up for late toxicity will cease when a patient experiences disease progression, since 2nd line therapies may then be initiated.

Non immune-related toxicity (SBRT-related toxicity) is defined as any toxicity observed within the tissues contained within the radiation portal and is consistent with tissue reaction to radiation exposure at any time during follow-up.

Immune-related toxicity is defined as an adverse event that is associated with exposure to ipilimumab and that is consistent with an immune phenomenon.

CONFIDENTIAL

This material is the property of the study sponsor. Do not disclose or use except as authorized in writing by the study sponsor

Printed on 1/31/2017

6 Study Procedures

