8.3 Endpoints

Toxicity: CTCAE version 4.0 grades will be employed. Any patient who receives any amount of radiotherapy or study medication will be included in the toxicity analysis.

Dose-limiting toxicity (DLT) is defined generally as associated with the treatment, and for ipilimumab, that the event must be consistent with an immune-related effect. DLT is experienced during study treatment or within 30 days after last injection of ipilimumab, as long as the patient has not started another systemic treatment for cancer and is defined more precisely in Section 5.2.

Maximum tolerated SBRT fraction (MTD) is defined as the SBRT fraction dose level at which 0-1/6 patients experience DLT and at least 2 patients treated at the next higher dose level experience DLT (or the apparent MTD is Dose level 1).

Late toxicity is defined generally as an adverse event associated with the treatment which occurs beyond 30 days after last injection (i.e., adverse events which are observed months after treatment are most likely associated with SBRT) and is defined more precisely in Section 5.2.

Response: Immune-related clinical response will be scored on a non-index lesion using immune-related response criteria (irRC) according to irRECIST 1.1 (48). Patients who do not complete a clinical response evaluation, with the exception of those patients with rapidly progressing disease, will be scored as unevaluable. The immune-related clinical response rate is defined as the proportion of patients treated at the MTD who achieve either a complete or partial immune-related response. Unevaluable patients are included in denominator for the calculation of the objective response rate.

Immunologic outcomes include: 1) analysis of lymphocyte subsets and lymphocyte activation, 2) analysis of antigen-specific T cells and 3) tumor-specific T cells, as described in Section 7.2.2. For T cell response analyses, overall immune response is defined as >2 fold pre-treatment/post-treatment increase in any of the key T cell parameters.

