10.2 Data and Safety Monitoring Plan

Institutional support of trial monitoring will be in accordance with the FHCRC/University of Washington Cancer Consortium Institutional Data and Safety Monitoring Plan. Under the provisions of this plan, FHCRC Clinical Research Support coordinates data and compliance monitoring conducted by consultants, contract research organizations, or FHCRC employees unaffiliated with the conduct of the study. Independent monitoring visits occur at specified intervals determined by the assessed risk level of the study and the findings of previous visits per the institutional DSMP.

The monitors are independent contractors and are external to the Cancer Consortium (University of Washington and Fred Hutchinson Cancer Research Center). Study monitors will perform ongoing source data verification to confirm that critical protocol data transcribed on the CRFs by authorized site personnel are accurate, complete, and verifiable from source documents. To facilitate source documentation verification, the investigator(s) and institution(s) must provide the Monitor direct access to applicable source documents and reports for trial-related monitoring, audits, and IRB/EC review. The investigational site must also allow inspection by applicable regulatory authorities.

In addition, protocols are reviewed at least annually and as needed by the Consortium Data and Safety Monitoring Committee (DSMC), FHCRC Scientific Review Committee (SRC) and the FHCRC/University of Washington Cancer Consortium Institutional Review Board (IRB). The review committees evaluate accrual, adverse events, stopping rules, and adherence to the applicable data and safety monitoring plan for studies actively enrolling or treating patients. The IRB reviews the study progress and safety information to assess continued acceptability of the risk-benefit ratio for human subjects. Approval of committees as applicable is necessary to continue the study.

The trial will comply with the standard guidelines set forth by these regulatory committees and other institutional, state and federal guidelines.

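### No pre-specified threshold covers an excess of severe immune-related events attributed to ipilimumab: the DLT definition filters them out, and no other toxicity rule has a number attached

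*Combined protocol and SAP*

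**What the plan says.** Section 5.2 sets the grades: "Dose-limiting (Acute) Toxicity is defined as any treatment related Grade 4 or higher immune-related toxicity or Grade 3 or higher non-immune related toxicity". The event must fall during treatment or within 30 days of the last ipilimumab injection. A bolded conjunction then adds that it must be one "which is probably or definitely related to radiation treatment". On its purpose, 5.2 says "This definition will be used for de-escalation to the -1 dose level". The same section states: "Immune-related toxicity is defined as an adverse event that is associated with exposure to ipilimumab".

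Section 8.3 describes DLT in general terms as associated with the treatment, adding "for ipilimumab, that the event must be consistent with an immune-related effect". It sets no radiation condition, but refers to 5.2 for the precise definition.

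Numeric action is tied to DLTs only: de-escalation in 8.4 and 8.4.1, and termination for DLTs at level -1 in 8.4.1.

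On the background rate, section 1.1 reports: "Grade 3 or 4 immune-related adverse events occurred in 10 to 15% of patients treated with ipilimumab". The Summary that closes section 1 gives the aim: to vaccinate with SBRT "and then to elaborate the induced immune response with the FDA-approved CTLA-4 blocking antibody ipilimumab".

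On oversight, section 9 calls for regular assessment of the number and type of SAEs, and 9.3 requires every SAE to be reported whatever its cause. For the DSMC, the Scientific Review Committee and the IRB, 10.2 states: "In addition, protocols are reviewed at least annually and as needed".

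**The concern.** The plan tests a combination but ties its only numeric safeguard to events individually attributed to one component, radiation. If SBRT raised the frequency of immune-related events on ipilimumab, a single case would look like the cases that ipilimumab alone produces in 10 to 15% of patients. The excess would show mainly as a rate, and the plan compares no such rate with a limit. Section 8.5 recognises the difficulty, promising to describe attribution to SBRT or ipilimumab only where that is possible.

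At stake is whether a raised rate of severe immune-related events, deaths included, is recognised against a criterion fixed in advance or only when someone reading individual reports judges it high. At the planned 15 patients per year, reviews held only at the annual minimum would fall about 15 patients apart in a 40-patient trial.

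**Working it through.** **1. Reproduce the plan's own figure.** The table in 8.4.2 is the probability of at most one DLT in six patients: P(X ≤ 1) = (1-p)^6 + 6p(1-p)^5. For p = 0.10, 0.20, 0.30, 0.40 and 0.50 this gives 0.886, 0.655, 0.420, 0.233 and 0.109. The table prints 0.89, 0.66, 0.42, 0.23 and 0.11; the remaining entries also agree. The table is correct for events that already satisfy 5.2. It says nothing about events that 5.2 screens out.

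**2. Put the attribution filter into the calculation.** Inputs:
- n = 20 patients per stratum (8.1).
- Trigger of two or more DLTs (8.4.1). Section 8.4 says one; the two must be reconciled.
- p, the true rate of Grade 4+ immune-related events. This is assumed: the documents give only 10 to 15% for Grade 3 or 4 on ipilimumab.
- a, the share of those events judged probably or definitely due to radiation. This is also assumed: the documents give no value.

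The counted rate from these events is q = p × a, and P(2+) = 1 - (1-q)^20 - 20q(1-q)^19.

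Worked case, p = 0.30 and a = 0.10: q = 0.03, and 1 - 0.5438 - 0.3364 = 0.12.

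| True Grade 4+ rate p | a = 0 | a = 10% | a = 25% | a = 100% |
|---|---|---|---|---|
| 10% | 0 | 0.02 | 0.09 | 0.61 |
| 15% | 0 | 0.04 | 0.17 | 0.82 |
| 30% | 0 | 0.12 | 0.45 | 0.99 |
| 40% | 0 | 0.19 | 0.61 | >0.99 |

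Under the one-DLT version in 8.4, the row p = 30% becomes 1 - (1-q)^20 = 0, 0.46, 0.79 and >0.99. With a = 0, neither version can trigger at any p. Grade 3 immune-related events add nothing in any column.

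**3. Check a count that ignores attribution.** Take all acute Grade 3-5 immune-related events over both strata, at 10, 20, 30 and 40 treated patients. The benchmark is 15%, the upper end of the protocol's range. The boundary at each look is the smallest k with P(X ≥ k | n, 0.15) ≤ 0.10:

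| n | k | P at k | P at k-1 |
|---|---|---|---|
| 10 | 4 | 0.050 | 0.180 |
| 20 | 6 | 0.067 | 0.170 |
| 30 | 8 | 0.070 | 0.153 |
| 40 | 10 | 0.067 | 0.135 |

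The exact probability of reaching a boundary at any look comes from carrying the binomial distribution of the count forward through the looks and removing the paths that have already crossed:

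| True Grade 3-5 rate | By patient 30 | By patient 40 |
|---|---|---|
| 10% | 0.023 | 0.025 |
| 15% | 0.12 | 0.14 |
| 20% | 0.31 | 0.37 |
| 25% | 0.56 | 0.65 |
| 30% | 0.77 | 0.85 |
| 40% | 0.97 | 0.99 |

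These figures assume independent patients whose acute window is complete at each look.

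**The case against.** The strongest reply is that oversight exists and does not depend on attribution. SAEs of any cause are reported as soon as possible (9.3), their number and type are regularly assessed (section 9), and the committees look at adverse events both yearly and when needed (10.2), with approval required to continue. A reader might infer from 5.2 that an excess of ipilimumab-attributed events could never lead to a review. The documents do not support that. What they lack is a threshold, not a route. Section 10.2 does ask the committees to evaluate stopping rules, but the only numeric ones are the DLT rules that exclude these events.

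Second, the radiation condition might attach only to the non-immune limb, and 8.3 points that way. This reading is weaker. The condition is parallel to the time window, which 8.3 applies to all DLTs. It would also add little to the non-immune limb, since 5.2 already labels that limb SBRT-related. Section 8.3 itself defers to 5.2. Even so, the two sections pull apart.

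Third, a reader might infer that the immune limb is empty, or that more immune toxicity is the expected result of the combination. Neither is documented. At a 25% share the limb has some force, and the aim in section 1 concerns anti-tumour response. Greater immune toxicity is plausible, but no rate for the combination is given. The six-patient criterion also makes the gap look starker than 20 patients per stratum do: at an assumed 40% rate and 10% share it passes with probability 0.978, against 0.233 if all events count.

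Finally, relying on institutional review is a defensible choice for an approved agent at its approved dose. That argues for a modest addition, not against one.

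**Conclusion.** The point holds as a gap in pre-specification. On the natural reading of 5.2, severe or fatal immune-related events attributed to ipilimumab alone fall outside every numeric rule, and Grade 3 immune-related events fall outside whatever their attribution. They still reach SAE reporting and committee review, with no criterion set in advance.

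The size cannot be fixed from the documents. At an assumed 30% Grade 4+ rate in one stratum, the chance that the two-DLT rule responds to these events runs from 0 to 0.99 as the share blamed on radiation runs from none to all. The plan gives no means of predicting that share: the causality scale in 9.2.2 is worded for study drug and has no probable or definite level. The conclusion rests on the radiation condition covering both limbs of the definition. If the sponsor intended otherwise, the gap narrows to Grade 3 events and to a contradiction between 5.2 and 8.3. The change should be made, but its absence does not leave the trial without safety oversight.

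**What to change.** 1. Reconcile the DLT wording in 5.2 and 8.3 so that it is clear whether the radiation condition applies to immune-related events. This review takes no position on which is right. The one-DLT and two-DLT triggers in 8.4 and 8.4.1 need the same treatment.

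2. Add a review-only trigger to 10.2, for example: 'Acute Grade 3-5 immune-related events, regardless of attribution to SBRT or ipilimumab, are counted over both strata after every 10 treated patients. If the count is at least 4 of 10, 6 of 20, 8 of 30 or 10 of 40 (each exact one-sided P ≤ 0.10 against 15%), the DSMC holds an unscheduled review.' The sponsor may choose another benchmark and recompute the counts. The rule prescribes no clinical action; that stays with the committee.

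The cost is protocol wording and at most four counts from adverse event data already collected, put to an existing committee. There is about a 14% chance of one unneeded review if the true rate is exactly 15%. The limits should be stated: the benchmark is a Grade 3-4 rate from previously treated patients, while this trial counts Grade 5 as well and also enrols untreated patients; detection of a moderate excess is limited (0.56 by patient 30 at a true 25%); and the look at 40 comes after accrual has ended.

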6.1 General Study Design

This is a stratified phase II (with allowance for a (-1) dose level) study of stereotactic body radiotherapy (SBRT) combined with immunotherapy for previously untreated or previously treated metastatic melanoma patients. Patients will undergo a short course of high dose SBRT to a single index lesion that measures 1 cm to 5 cm. These fractions will be administered several days apart. Radiotherapy will be immediately followed by ipilimumab, at the FDA-approved dose and schedule.

6.2 Stereotactic Body Radiation Therapy

All subjects will be immobilized in a custom designed device in the appropriate position to isolate the index lesion. Radiotherapy treatment planning CT scans (with contrast, unless contraindicated) will be required to define the gross target volume (GTV) and planning target volume (CTV). The treatment planning CT scan should be acquired with the subject in the same position and using the same immobilization device as for treatment. Treatment planning will be done using a 3D based CT treatment planning system. All tissues to be irradiated must be included in the CT scan. Planning CT scan will be done at 3 mm intervals from encompassing the region of interest with sufficient margin for treatment planning.

6.2.1 Stereotactic Targeting and Treatment

SBRT has now been formally defined and described in a published guideline from the American College of Radiology and American Society for Therapeutic Radiology and Oncology (Potters 2004). This protocol will respect that guideline. The term stereotactic, for the purposes of this protocol, implies the targeting, planning, and directing of therapy using beams of radiation along any trajectory in 3-D space toward a target of known 3-D coordinates. The coordinate system is defined by reliable "fiducial" markers. This differs from conventional radiation therapy, in which therapy is directed toward less-than-reliable skin marks or bony landmarks that are indirectly referenced to the tumor (surrogates). This protocol will require treatments to be conducted with the use of a fixed 3-D coordinate system defined by fiducials. The coordinate system defined by the fiducials should be directly related to the radiation-producing device in a reproducible and secure fashion. Capability should exist to define the position of targets within the patient according to this same 3-D coordinate system. As such, the patient is set up for each treatment with the intention of directing the radiation toward a target according to the known 3-D coordinates as determined in the process of treatment planning. The nature of the fiducials themselves may include radiopaque markers or rods placed at known locations in a frame or fixed structure adjacent to the patient as well as use of the tumor itself as a fiducial (e.g., acquiring tomographic views of the tumor simultaneously with the treatment). Metallic "seeds" placed within the tumor will be allowed to constitute a fiducial so long as the methods are validated and a plan is in place to identify seed migration (e.g., redundant seeds placed).

6.2.2 Target Contouring

Gross Tumor Volume (GTV) is defined as all known gross disease encompassing the selected index lesion. The GTV will consist of the index lesion as visualized on CT.

Internal Gross Tumor Volume (IGTV) is defined for mobile index lesions at the discretion of the treating physician. A 4-D CT scan will be acquired in order to account for the motion of the lesion during. The IGTV will be defined as the union of the visualized index lesion on all gated CT data sets.

CONFIDENTIAL

This material is the property of the study sponsor. Do not disclose or use except as authorized in writing by the study sponsor

Printed on 1/31/2017

Planning Target Volume (PTV) will be defined as per the convention for photon beam radiotherapy. A 3-dimensional margin will be created on the GTV or IGTV (if available) to allow for daily set-up variance.

6.2.2 Normal Structures

Organ at risk volume (OAR) is contoured as visualized on the planning CT or MR scan. Planning PAR is the OAR expanded for setup uncertainty or organ motion. The physician will contour the OAR. The dosimetrist will create the PAR by expanding the OAR by 2-3 mm, depending on the situation.

6.2.3 Dose fractionation and specification

The prescription dose per fraction to the PTV will be 8 Gy per fraction for a bone or lung index lesion and 6Gy per fraction for any liver or subcutaneous index lesion.

The total dose for dose level 1 (our starting dose level) will be one will be 24Gy over 3 fractions for a bone or lung index lesion and 18Gy over three fractions for any liver or subcutaneous index lesion.

If we encounter a dose limiting toxicity, we will then reduce our total dose to dose level -1. The total dose for dose level -1 will be 16Gy over 2 fractions for a bone or lung index lesion and 12Gy over two fractions for any liver or subcutaneous index lesion.

Dose rate: For the purpose of this study, dose rate utilized will be that which is commissioned by the manufacturer and the medical physics group for external beam radiotherapy delivery by the University of Washington Department of Radiation Oncology. There will be no special dose rate modifications required for this study.

